## 4 STUDY CONDUCT

### 4.1 Intervention Assignment

The advanced metastatic cancer portion of this study is not randomized. Treatment assignment will be based on the percentage of tumoral CD8 cells at the initial biopsy. Participants who have a tumor with  $\geq 15\%$  CD8 cells will receive nivolumab monotherapy, and participants who have a tumor with  $< 15\%$  CD8 cells will receive ipilimumab in combination with nivolumab.

Approximately 20 advanced prostate cancer participants who have a tumor with < 15% CD8 cells will be randomly allocated to receive nivolumab 1 mg/kg in combination with ipilimumab 3 mg/kg (Prostate Cohort A) or nivolumab 1 mg/kg in combination with ipilimumab 5 mg/kg (Prostate Cohort B) in a 1:1 ratio. All advanced prostate cancer participants who have a tumor with  $\geq$  15% CD8 cells will receive nivolumab monotherapy. Participants who are randomly allocated but do not receive study intervention for any reason may be replaced. Randomization will be performed by the Sponsor.

Study intervention will be administered by site personnel and tracked using drug accountability records.

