6.3 MEASURES TO MINIMIZE BIAS: RANDOMIZATION AND BLINDING

6.3.1 Intervention Assignment

The advanced metastatic cancer portion of this study is not randomized. Treatment assignment will be based on the percentage of tumoral CD8 cells at the initial biopsy. Participants who have a tumor with $\geq 15\%$ CD8 cells will receive nivolumab monotherapy, and participants who have a tumor with $< 15\%$ CD8 cells will receive ipilimumab in combination with nivolumab.

The first 10 advanced prostate cancer participants who enroll with a tumor with $< 15\%$ CD8 cells will be randomly allocated to receive nivolumab 1 mg/kg in combination with ipilimumab 3 mg/kg (Prostate Cohort A) or nivolumab 1 mg/kg in combination with ipilimumab 5 mg/kg (Prostate Cohort B) in a 1:1 ratio.

The remaining 10 advanced prostate cancer participants will not be randomly allocated but instead assigned to an intervention cohort based on the safety observed in both cohorts. If Prostate Cohort B is determined to have a tolerable safety profile (per [Section 6.6.1.4](#)), the remaining 10 advanced prostate cancer participants will be assigned to Prostate Cohort B. If the safety profile of Prostate Cohort B is deemed unacceptable, the remaining 10 advanced prostate cancer participants will be assigned to Prostate Cohort A.

All advanced prostate cancer participants who have a tumor with $\geq 15\%$ CD8 cells will receive nivolumab monotherapy. Participants who are randomly allocated but do not receive study intervention for any reason may be replaced. Randomization will be performed by the Sponsor.

Study intervention will be administered by site personnel and tracked using drug accountability records.

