50	10	5	(3.7, 19.9)
40	10	4	(3.2, 21.2)
30	10	3	(2.6, 23.2)
160	20	32	(14.2, 26.5)
125	20	25	(13.5, 27.4)
100	20	20	(12.9, 28.3)
75	20	15	(11.9, 29.6)
50	20	10	(10.4, 31.8)
40	20	8	(9.5, 33.2)
30	20	6	(8.3, 35.2)
160	30	48	(23.1, 37.1)
125	30	38	(22.6, 38.5)
100	30	30	(21.4, 39.0)
75	30	22	(19.6, 39.6)
50	30	15	(18.1, 42.6)
40	30	12	(16.9, 44.0)
30	30	9	(15.2, 46.0)

A total of approximately 20 advanced prostate cancer participants with CD8 low tumors will be treated with the combination of nivolumab and ipilimumab, in 1 of 2 dosing cohorts. The first 10 participants enrolled will be randomly allocated by the Sponsor into one of two cohorts (5 participants per cohort) to evaluate the safety of different dose levels of ipilimumab in combination with nivolumab. If the higher dose level (ipilimumab 5 mg/kg + nivolumab 1 mg/kg) is determined to be tolerable per [Section 6.6.1.4](#), an additional 10 participants will be enrolled at this higher dose level (Prostate Cohort B). If the safety profile of Prostate Cohort B is deemed unacceptable, an additional 10 participants will be enrolled at the lower dose level (Prostate Cohort A).

We hypothesize that higher doses of ipilimumab will demonstrate a larger proportion of participants who convert from CD8 low to CD8 high. There is no prior for the expected proportion of participants who will convert from CD8 low to CD8 high at the various dose levels of ipilimumab. With 15 participants enrolled in Prostate Cohort B, Table 12 provides 95% credible intervals for possible CD8 conversion rates in the cohort. For example, a 95% credible interval assuming 6/15 (40%) participants converting in the cohort would be (17.7%, 64.9%).

Table 12: Credible Intervals for CD8 Conversion

Subgroup Size	CD8 Conversion Rate	Expected Successes	95% Credible Interval
15	20	3	(4.7, 42.8)
15	40	6	(17.7, 64.9)
15	60	9	(35.1, 82.3)

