Up to 200 participants with advanced metastatic cancer could be enrolled. A total of 20 participants with advanced prostate cancer and tumoral CD8 < 15% could be enrolled into the Advanced Prostate Cancer portion of the study (10 per treatment arm).

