#### **4.4 Safety Monitoring for Advanced Prostate Cancer**

As the combination regimen with ipilimumab 5 mg/kg has not been extensively studied, in addition to adverse events being reviewed by the Sponsor on an ongoing basis and investigator meetings convening approximately every 2 weeks to discuss and review safety events, a safety pause is included after the 5th patient has initiated treatment with ipilimumab at the 5 mg/kg dose level.

Enrollment will pause until all participants have been followed for at least 6 weeks. The safety pause will apply to both cohorts to preserve random allocation; however, the safety assessment as follows will apply to the ipilimumab 5 mg/kg cohort specifically. The initial 5 participants enrolled in the ipilimumab 5 mg/kg cohort will be observed for the occurrence of treatment-related adverse events (TRAEs) necessitating discontinuation of both agents from the beginning of treatment through completion of the first cycle (ie, 6 weeks).

If 3 or fewer of the first 5 participants in the ipilimumab 5 mg/kg cohort experience a TRAE leading to discontinuation of both agents, enrollment for that specific cohort will continue as planned until a total of approximately 10 participants are enrolled. If 4 or more of the first 5 participants of the ipilimumab 5 mg/kg cohort experience a TRAE leading to discontinuation of both agents, enrollment into the cohort will be suspended, and an ad hoc safety review (conducted by Investigators and Sponsor representatives) will be performed to assess the available data and provide a recommendation, which may include, but is not limited to, modification or discontinuation of the cohort, and will be documented in the study records. Only TRAEs leading to treatment discontinuation of both agents occurring up until the 5th

participant in each cohort completes Cycle 1 will be included—dose delays for adverse events not otherwise meeting criteria at that time will not be counted. The stopping rule was chosen as this corresponds to a > 80% chance that the toxicity rate in the cohort is > 40%, assuming a beta (0.8, 1.2) prior.

Should the ipilimumab 5 mg/kg cohort demonstrate 6 or greater treatment-related adverse events requiring discontinuation of therapy at any time, enrollment will be suspended until an ad hoc safety review convenes and provides a recommendation, as described above.

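### The SAP's prostate sections contradict the current protocol on randomisation, cohort size, the step after the five-participant safety check and the suspension count, and SAP section 6 discloses none of it

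*SAP*

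**What the plan says.** **Allocation.** SAP 4.1: "Approximately 20 advanced prostate cancer participants who have a tumor with < 15% CD8 cells will be randomly allocated", in a 1:1 ratio to Cohort A (ipilimumab 3 mg/kg) or Cohort B (5 mg/kg). Protocol 6.3.1 randomises the first 10 only, and then: "The remaining 10 advanced prostate cancer participants will not be randomly allocated but instead assigned to an intervention cohort".

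**Cohort size.** SAP 3 describes the prostate "portion of the study (10 per treatment arm"). Protocol 9.1 plans 5 per cohort and then 10 more in one of them: "With 15 participants enrolled in Prostate Cohort B, Table 12 provides 95% credible intervals for possible CD8 conversion rates in the cohort".

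**After the first five in Cohort B.** The trigger is the same in both documents: 3 or fewer of 5, against 4 or more, with a treatment-related event that stops both drugs. The action differs. SAP 4.4 says that after 3 or fewer "enrollment for that specific cohort will continue as planned until a total of approximately 10 participants are enrolled", and after 4 or more "enrollment into the cohort will be suspended, and an ad hoc safety review" follows. Protocol 6.6.1.4 enrols the next 10 in B in the first case and in A in the second.

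**Later suspension.** SAP 4.4: "Should the ipilimumab 5 mg/kg cohort demonstrate 6 or greater treatment-related adverse events requiring discontinuation of therapy at any time", enrolment is suspended. Protocol 6.6.1.4 sets the count at 8 and applies it to either prostate cohort.

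**Synopsis and disclosure.** SAP 3.1 presents SAP 8.1 as the protocol synopsis. SAP 8.1 has the whole CD8 low prostate group randomised, whereas the current synopsis (protocol 1.1) randomises about 10. SAP section 6 lists one difference from the protocol, concerning baseline CD8 and its association with CBR and OS.

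**The concern.** For the same 20 or so participants, the two documents give two allocation schemes, two sets of cohort sizes, two follow-on actions and two suspension counts. A reader who relies on SAP section 6 would conclude that the prostate design is as the protocol has it.

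Two things are at stake. The first is the description of the design: under the protocol half the group is not randomised, and the SAP says all of it is. The second is a safety threshold for a regimen that both documents describe as not extensively studied, in a trial without an independent monitoring committee. The SAP also sets no suspension count for Cohort A, although under the protocol that cohort could grow to 15.

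**Working it through.** **Side by side, current text only**

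| Item | SAP | Protocol |
|---|---|---|
| Randomised | about 20 (4.1) | first 10 (6.3.1) |
| Cohort sizes | 10 and 10 (3) | 5 + 5, then 10 in one: 15 and 5 (9.1) |
| 3 or fewer of 5 | fill B to about 10 (4.4) | next 10 to B (6.6.1.4) |
| 4 or more of 5 | suspend B, ad hoc review (4.4) | next 10 to A (6.6.1.4) |
| Later suspension | 6, 5 mg/kg cohort only (4.4) | 8, either cohort (6.6.1.4) |

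**Toxicity rule.** Both documents justify the rule by saying that it "corresponds to a > 80% chance that the toxicity rate in the cohort is > 40%, assuming a beta (0.8, 1.2) prior". With x events in n participants, the posterior probability is

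Pr(θ > 0.40 | x, n) = 1 − F(0.40; 0.8 + x, 1.2 + n − x), where F is the beta distribution function.

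The plan's own figure comes first. At n = 5, 3 events give 0.776 and 4 events give 0.942, so 4 is the first count above 0.80, as stated.

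The same criterion was then applied to the later counts:

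| n | Count just below | Smallest count above 0.80 |
|---|---|---|
| 5 | 3: 0.776 | 4: 0.942 |
| 10 | 5: 0.714 | 6: 0.878 |
| 15 | 7: 0.681 | 8: 0.834 |

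So 6 fits a cohort of 10 and 8 fits a cohort of 15. Six events in 15 participants give only 0.487. If the true rate is 40%, the binomial probability of at least 6 of 15 is 0.597, against 0.213 for at least 8 of 15.

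Two assumptions apply. The documents attach the 80% rationale to the 4-of-5 rule, so extending it to 6 and 8 is my reading. Both later rules count events, so treating them as participants assumes one event each.

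**Planning precision for CD8 conversion.** The protocol states that there is no prior. The 2.5% and 97.5% quantiles of Beta(x, n − x) reproduce all three rows of protocol Table 12:

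- 3/15: (4.7, 42.8)
- 6/15: (17.7, 64.9)
- 9/15: (35.1, 82.3)

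At 40% conversion, the interval for each possible cohort size is:

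- 6/15: (17.7%, 64.9%), width 64.9 − 17.7 = 47.2 points
- 4/10: (13.7%, 70.1%), width 70.1 − 13.7 = 56.4 points
- 2/5: (6.8%, 80.6%), width 80.6 − 6.8 = 73.8 points

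Only the first appears in the documents. The SAP states no precision target for the prostate cohorts.

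**Origin.** SAP 3 labels the prostate part with Protocol Amendment 3, and the protocol's revision summary attributes these design changes to Amendment 5. The SAP was probably written to the older design. Its date is not visible in the text supplied, so this is an inference.

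**The case against.** The facts are not in dispute; their weight is. Allocation and suspension are conduct rules, and a design change needs ethics approval, so SAP text cannot alter them. The clause in protocol 9.4 that gives the SAP precedence sits under statistical analyses, and SAP 2 limits supersession to analyses. CBR, ORR and conversion are estimated within group or analysis population, in the same way at 15/5 or 10/10. SAP 5.4 rules out powered comparisons between groups. SAP 3.3 refers the reader to protocol 9.1 for sample size, where the current plan stands. If the SAP predates Amendment 5, section 6 could not have listed differences that did not yet exist. On this view the mismatch is minor and clerical.

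Most of this stands, and it is why the impact is modest. It does not remove the conflict. The cross-reference leads a reader to 15 and 5 after SAP 3 has said 10 and 10, and it does nothing for SAP 4.1 or 4.4. A wrong allocation scheme and a wrong safety count go beyond clerical slips, whatever their origin.

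The objection also has a point about SAP 5.2. Its combined enrolled/randomized label covers the whole study, most of which is not randomised, so it is no evidence of a prostate-specific defect. Splitting that row is optional.

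**Conclusion.** The concern holds and should be fixed. All four conflicts are in current operative text, and SAP section 6 lists none of them. In size: 10 participants randomised against about 20; cohorts of about 15 and 5 against 10 and 10; suspension at 8 events in either cohort against 6 in the 5 mg/kg cohort only; and a different action on both branches of the five-participant check.

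No estimator changes, and the protocol most naturally governs conduct. What remains is a misdescribed design and a conflicting safety threshold in the analysis document. The match of 6 to n = 10 and 8 to n = 15 rests on the two assumptions given with the calculation. The textual conflicts do not depend on them.

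**What to change.** Bring SAP 3, 4.1, 4.4 and 8.1 into line with the current protocol:

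- First 10 randomised, 5 per cohort.
- Next 10 assigned without randomisation: to B after 3 or fewer of 5, to A after 4 or more.
- Final sizes about 15 and 5.
- Suspension at 8 events in either cohort.

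State that the prostate cohorts are only partly randomised, and identify the 10 non-randomised participants in the cohort summaries. A split row in the SAP 5.2 disposition table is an optional way to do this.

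If 6 is meant to be kept for the 5 mg/kg cohort, put it in the protocol and list it in SAP section 6.

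When editing SAP 8.1, keep its 3 mg/kg crossover dose. It agrees with protocol Figure 3 and section 6.1, whereas the current protocol synopsis gives 5 mg/kg, so the synopsis should not be copied wholesale.

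The cost is text edits to four SAP sections and, if wanted, one table row. Adopting 8 drops the earlier pause written into the SAP for the 5 mg/kg cohort, and the tables will show that only 5 per cohort were randomised.

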#### **4.2 Blinding**

This is an open-label trial; therefore, the Sponsor, Investigator, and participant will know the study intervention administered.

#### **4.3 Safety Monitoring for Advanced Metastatic Cancer**

The safety of nivolumab and ipilimumab therapies will be monitored during the trial as per the interim analyses described in [Section 5.9](#).

#### **4.4 Safety Monitoring for Advanced Prostate Cancer**

As the combination regimen with ipilimumab 5 mg/kg has not been extensively studied, in addition to adverse events being reviewed by the Sponsor on an ongoing basis and investigator meetings convening approximately every 2 weeks to discuss and review safety events, a safety pause is included after the 5th patient has initiated treatment with ipilimumab at the 5 mg/kg dose level.

Enrollment will pause until all participants have been followed for at least 6 weeks. The safety pause will apply to both cohorts to preserve random allocation; however, the safety assessment as follows will apply to the ipilimumab 5 mg/kg cohort specifically. The initial 5 participants enrolled in the ipilimumab 5 mg/kg cohort will be observed for the occurrence of treatment-related adverse events (TRAEs) necessitating discontinuation of both agents from the beginning of treatment through completion of the first cycle (ie, 6 weeks).

If 3 or fewer of the first 5 participants in the ipilimumab 5 mg/kg cohort experience a TRAE leading to discontinuation of both agents, enrollment for that specific cohort will continue as planned until a total of approximately 10 participants are enrolled. If 4 or more of the first 5 participants of the ipilimumab 5 mg/kg cohort experience a TRAE leading to discontinuation of both agents, enrollment into the cohort will be suspended, and an ad hoc safety review (conducted by Investigators and Sponsor representatives) will be performed to assess the available data and provide a recommendation, which may include, but is not limited to, modification or discontinuation of the cohort, and will be documented in the study records. Only TRAEs leading to treatment discontinuation of both agents occurring up until the 5th

participant in each cohort completes Cycle 1 will be included—dose delays for adverse events not otherwise meeting criteria at that time will not be counted. The stopping rule was chosen as this corresponds to a > 80% chance that the toxicity rate in the cohort is > 40%, assuming a beta (0.8, 1.2) prior.

Should the ipilimumab 5 mg/kg cohort demonstrate 6 or greater treatment-related adverse events requiring discontinuation of therapy at any time, enrollment will be suspended until an ad hoc safety review convenes and provides a recommendation, as described above.

## 5 STATISTICAL ANALYSIS

Summary statistics will be presented by study intervention group. Categorical variables will be summarized using frequencies and percentages. Continuous variables will be summarized using means, standard deviations, medians, interquartile ranges (IQR; 25th to 75th percentile), minimums, and maximums.

### 5.1 Populations for Analysis

For purposes of analysis, the following populations are defined (Table 2):

**Table 2: Populations for Analysis**

| Population                                 | Description                                                                                                                                                                                                                      |
|--------------------------------------------|----------------------------------------------------------------------------------------------------------------------------------------------------------------------------------------------------------------------------------|
| Safety Population                          | All participants who received at least one dose of study drug. Participants will be analyzed according to the study intervention actually received.                                                                              |
| Modified Intent-to-Treat (mITT) Population | All participants with sufficient biopsy results to be assigned to a treatment arm and who received at least 1 dose of study drug. Participants will be analyzed according to the study intervention to which they were assigned. |
| On-treatment Biopsy Population             | All participants with at least 1 on-treatment biopsy with sufficient CD8 results will be included in the analyses of changes in CD8 counts.                                                                                      |

### 5.2 Analysis of Study Conduct

The number of participants who were screened, enrolled/randomized, treated, and completed the study will be presented in a summary table. The reason for treatment discontinuation and study discontinuation will also be summarized.

The participant time on treatment and time on study will be presented in a summary table. Time on treatment is defined as the date from first dose of study intervention until the date of last dose of study intervention. Time on study is defined as the date from first dose of study intervention until the date of death or last contact. The number of participants currently on

treatment and study will be presented along with the median time on treatment/study and the associated range. Time on treatment will be calculated using the Kaplan-Meier method, where participants who have discontinued treatment are considered to have an event and participants remaining on treatment are censored at their most recent treatment date. Time on study will be calculated using the reverse Kaplan-Meier method, where participants who remain on study (active treatment or in follow-up) are considered to have an event and participants who died or have discontinued the study are censored at their death or end of study date.

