7.3 LOST TO FOLLOW-UP

A participant will be considered lost to follow-up if he or she repeatedly fails to return for scheduled visits and is unable to be contacted by the study site.

The following actions must be taken if a participant fails to return to the clinic for a required study visit:

- The site must attempt to contact the participant and reschedule the missed visit as soon as possible and counsel the participant on the importance of maintaining the assigned visit schedule and ascertain whether or not the participant wishes to and/or should continue in the study.
- Before a participant is deemed lost to follow-up, the Investigator or designee will make every effort to regain contact with the participant (where possible, 3 telephone calls and, if necessary, a certified letter to the participant's last known mailing address or local equivalent methods). These contact attempts should be documented in the participant's medical record or study file.
- Should the participant continue to be unreachable, he/she will be considered to have withdrawn from the study.

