### 3.4 Analysis Timing

Analysis for the Advanced Metastatic Cancer and Advanced Prostate Cancer portions will be performed independently and at different times due to differences in enrollment timelines.

The analysis of complete data for the clinical study report (CSR), described in the main body of this document, will be performed after all participants have been followed for at least 9 months or have discontinued early from the study, and all data from the study through the clinical cutoff date have been entered and reviewed for completeness.

Analysis of efficacy and safety endpoint may be performed prior to the CSR analysis. These results may be presented and/or published prior to the CSR analysis.

The study will formally end once all participants have either completed the safety and survival follow-up periods or have discontinued early from the study, all data from the study are entered in the clinical database, and the clinical database is locked.

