#### 5.4.2.3 Overall Survival

Overall Survival (OS) is defined as the time from initiation of study intervention until death due to any cause. Participants who are not reported as having died at the time of analysis will be censored at the most recent contact date they were known to be alive. See Section 5.8.2 for handling of missing or partial death dates.

OS will be estimated using Kaplan-Meier techniques, and the median survival time and 95% CIs will be estimated within each study intervention group.

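### The reverse Kaplan-Meier rule in SAP 5.2 censors participants who left the study as well as those who died, so median time on study may be overstated if there is attrition

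*SAP*

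**What the plan says.** SAP 5.2 (Analysis of Study Conduct) gives the definition first: "Time on study is defined as the date from first dose of study intervention until the date of death or last contact". The estimator follows: "Time on study will be calculated using the reverse Kaplan-Meier method". For that estimator, "participants who remain on study (active treatment or in follow-up) are considered to have an event", whereas "participants who died or have discontinued the study are censored at their death or end of study date".

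Three other places bear on the rule:

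- **SAP 5.4.2.3 (Overall Survival).** Participants not reported as dead "will be censored at the most recent contact date they were known to be alive". This covers withdrawals and losses as well as ongoing participants.
- **Protocol 7.3 (Lost to Follow-up).** "Should the participant continue to be unreachable, he/she will be considered to have withdrawn from the study". Lost participants therefore fall among those who discontinued the study.
- **SAP 3.4 (Analysis Timing).** The clinical study report (CSR) analysis is "performed after all participants have been followed for at least 9 months or have discontinued early from the study". The end of the study is defined separately: "The study will formally end once all participants have either completed the safety and survival follow-up periods or have discontinued early from the study".

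**The concern.** The duration defined in SAP 5.2 ends at death or last contact. For a participant who leaves the study alive, that duration is complete on the day of last contact. Coding it as censored tells the estimator that the true value is longer and unknown. The resulting curve describes how long participants could have been followed had nobody left, under a label and a definition that refer to how long they were followed.

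What is at stake is one descriptive figure. A reader uses median time on study to judge how mature the survival data are, and OS is the endpoint most closely tied to it because OS is also censored at last contact. A figure that does not fall as participants leave cannot show that follow-up was lost. SAP 3.4 foresees early discontinuations at the CSR analysis, so the affected group is not hypothetical, although its size is unknown.

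**Working it through.** The plan states no follow-up figure, so there is nothing to reproduce. The check has four steps.

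**1. Who is an event under each rule**

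| Status at cutoff | OS (SAP 5.4.2.3) | Reverse of the OS indicator | SAP 5.2 rule |
|---|---|---|---|
| Died | event | censored | censored |
| Alive, still on study | censored | event | event |
| Withdrawn or lost | censored | event | **censored** |
| Completed survival follow-up | censored | event | **not stated** |

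The SAP 5.2 rule differs from the reverse of the SAP's own OS coding in the third row and leaves the fourth open.

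**2. Direction**

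The estimate is S(t) = ∏(1 − dᵢ/nᵢ) over event times up to t. Take the end-of-study date of a withdrawn participant as the last contact date. The times and the risk sets nᵢ are then the same under both codings. Recoding a withdrawal from event to censored replaces a factor below 1 by a factor of 1. So S under the SAP rule is never below S under the reversed-OS coding, and its median is the same or later.

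A ten-participant example shows the mechanism. Months on study are 2 (died), 3 (withdrew), 4 (withdrew), 5 (died), 6 (withdrew), 8 (on study), 10 (died), 12, 14 and 16 (all on study).

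- Withdrawals as events: 8/9 × 7/8 × 5/6 × 4/5 = 0.519 at month 8. Multiplying by 2/3 gives 0.346 at month 12. The median is 12 months.
- SAP rule: 4/5 = 0.800 at month 8, × 2/3 = 0.533 at month 12, × 1/2 = 0.267 at month 14. The median is 14 months.

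**3. Size, by simulation**

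Inputs from the documents: minimum follow-up of 9 months (SAP 3.4), and group sizes of 40, 160 and 200 (Protocol 9.1). Assumed, and not in the documents: uniform accrual over 24 months, exponential OS with median 9, 12 or 24 months, and exponential withdrawal of 0% to 30% per year. There were 400 runs per setting, with both codings applied to the same data. Results for N = 160 and median OS of 12 months:

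| Withdrawal per year | Share withdrawn | Withdrawals as events (months) | SAP rule (months) | Difference (months, from unrounded medians) |
|---|---|---|---|---|
| 0% | 0% | 21.0 | 21.0 | 0.0 |
| 5% | 5% | 20.0 | 21.0 | 1.0 |
| 10% | 10% | 19.1 | 21.0 | 2.0 |
| 20% | 19% | 16.5 | 20.8 | 4.3 |
| 30% | 28% | 14.4 | 20.9 | 6.5 |

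Over all three group sizes and all three OS medians, the differences were 0.9 to 1.1 months at 5%, 1.9 to 2.3 at 10%, 4.2 to 4.7 at 20% and 6.3 to 6.9 at 30%. The SAP median was at or above the other in every run. It stays near 21 months because that is the assumed median time from first dose to cutoff: 9 + 24/2 = 21.

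**4. When nobody remains on study**

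The SAP 5.2 event requires a participant to be on treatment or in follow-up. At the formal study end in SAP 3.4, surviving participants have completed follow-up or discontinued. Every dᵢ is then 0, S(t) stays at 1 and the median does not exist. The CSR analysis may come earlier, so this affects a final table more than the CSR. The estimate can also fail earlier in a small group: with N = 40, median OS of 9 months and 30% withdrawal per year, 12% of runs had no estimable median under the SAP rule.

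**The case against.** Potential follow-up, from first dose to data cutoff, is an interpretable quantity, and a sponsor may choose to report it. Treating withdrawals as censored for that purpose makes the same kind of independence assumption that any reverse Kaplan-Meier makes for deaths. Dropout is also not hidden: SAP 5.2 requires the numbers treated and completed, the reasons for study discontinuation, the number currently on study, and the range. Attrition may be low, because stopping treatment is not leaving the study and Protocol 7.2 continues survival follow-up by telephone, records or visits.

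Much of this stands. It limits the importance of the point and its likely size. It does not rescue the rule, because the SAP does not say that it wants potential follow-up and defines time on study as ending at death or last contact. The accompanying counts give context but do not correct the median.

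Three stronger readings are tempting and are not supported:

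- **That the median is overstated whatever happens.** If nobody withdraws or is lost before the median, the two codings agree.
- **That the overstatement has a known size.** Withdrawal rate, accrual period and median OS are all absent from the documents.
- **That efficacy results, or the maturity of clinical benefit rate (CBR) and progression-free survival (PFS), are compromised.** CBR, objective response, CD8 conversion, PFS and OS each have their own rules. SAP 5.4.1 counts stable disease last assessed before 6 months as no benefit, and SAP 5.4.2.2 censors PFS without progression at a tumor assessment. Even a corrected time on study would not measure PFS follow-up.

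**Conclusion.** The point holds as a minor inconsistency within the SAP. The reverse Kaplan-Meier rule matches neither the SAP's definition of time on study nor the reverse of its OS censoring. The direction is certain: with attrition, the reported median is at or above the median of observed follow-up. The size is conditional. Under the assumed inputs it runs from 0 with no withdrawals, through about 1 month at 5% per year and about 2 months at 10%, to about 4 to 5 months at 20%. Read literally, the rule gives no median once nobody remains on study. The consequence is confined to one descriptive summary, which matters mainly for reading the maturity of OS.

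**What to change.** Replace the event and censoring sentence for time on study in SAP 5.2 with: *Participants who died are censored at the date of death; all participants alive at last contact (ongoing, completed follow-up, withdrawn or lost to follow-up) are counted as events at their last contact date.*

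Naming those who completed follow-up closes the gap in the current wording and keeps the rule usable at study end. If the sponsor also wants potential follow-up, it should appear under that name beside the observed figure.

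The cost is one sentence. No new data are needed and no efficacy analysis changes. Where participants have left the study, the reported median will usually be shorter.
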